5.6 Test Drug Concentration

Not applicable for this study.

5.7 Other Measurements, Assessments or Methods

5.7.1 Blood Sample for Molecular Profiling of CTCs

Whole blood samples will be collected at Week 1, Week 13 and at the time of PSA progression and/or at the time of radiographic progression. Seventeen milliliters (17 mL) of

- CONFIDENTIAL -

whole blood in two 8.5 mL ACD Sol A tubes are needed at each time point to ensure at least 5 mL for AR and GR analysis. Samples will be collected on Monday-Thursday and shipped overnight to for testing per vendor instructions. Remaining samples may be stored for future biomarker analysis. Methods as described by Antonarakis et al., 2014 will be used to capture CTC and quantification of messenger RNA (mRNA) of AR-FL, AR variants and GR-FL via Quantitative reverse-transcriptase–polymerase-chain-reaction (RT-PCR) assays. AR DNA was polymerase chain reaction-amplified and the product will be analyzed.

5.7.2 Serum Sample for Biomarker Analysis

Serum samples collected at Week 1, Week 13, and at the time of PSA progression and/or at the time of radiographic progression, will be shipped to a central lab for testing for, but not limited to, the analysis of inflammatory proteins such as IL6, IL8, TNF- α , soluble TNF1, etc. and neuroendocrine markers such as chromogranin A (CgA), neuron specific enolase (NSE), and synaptophysin. Five milliliters of blood will be collected to yield approximately 2 mL of serum. Remaining samples may be stored for future biomarker analysis.

5.8 Total Amount of Blood

The total amount of blood collected for routine laboratory tests and correlative biomarker analysis for each subject will vary depending on how long they stay on treatment. The maximum amount of blood collected for a subject within 24 hours during the treatment period is approximately 37 mL, including 15 mL for routine lab (i.e., CBC with differential, PSA, and comprehensive metabolic panel), and 22 mL for correlative biomarker analysis (Section 5.7). Furthermore, if any laboratory abnormalities are found for a subject, additional blood may be drawn for monitoring.

6 DISCONTINUATION

6.1 Discontinuation of Individual Subject(s)

A discontinuation is a subject who enrolled in the study and for whom study treatment is permanently discontinued prematurely for any reason.

The subject is free to withdraw from the study treatment and/or study for any reason and at any time without giving reason for doing so and without penalty or prejudice. The investigator is also free to terminate a subject's involvement in the study at any time if the subject's clinical condition warrants it.

If a subject is discontinued from the study with an ongoing adverse event or an unresolved laboratory result that is significantly outside of the reference range, the investigator will attempt to provide follow-up until the condition stabilizes or no longer is clinically significant.

The following events will result in the removal of subjects from enzalutamide therapy:

- Subject develops an adverse event, intercurrent illness, or toxicity, where continued
 administration of study drug is deemed not in the subject's best interest by the
 investigator and/or the sponsor. For example,
 - o Seizure;
 - Posterior Reversible Encephalopathy Syndrome;
 - Laboratory abnormality defined by protocol as follows:
 Creatinine > 354 μmol/L (> 4.0 mg/dL);
 - o AST, ALT, or total bilirubin > 5 times ULN;
 - o Absolute neutrophil count $< 750/\mu$ L;
 - o Platelet count < 50,000/mL.
- Decision by the investigator and subject to initiate a new anti-neoplastic therapy;
- Gross noncompliance with protocol: The medical monitor or investigator may request permanent treatment discontinuation in the event of a major protocol deviation such as administration of prohibited concomitant medication, lack of cooperation, or noncompliance.

Unless the subject withdraws consent, all subjects discontinuing study drug for any reason will have a Safety Follow-up visit 30 days after their last dose of study drug or prior to initiation of subsequent anti-neoplastic therapy for prostate cancer, whichever occurs first.

Subjects that discontinue study drug for a reason other than radiographic progression or initiation of a new anti-neoplastic therapy will have a PSA test performed 30 days from date of last dose and undergo long-term follow-up every 12 weeks from date of last dose. Long term follow-up will assess for survival, subsequent anti-neoplastic therapy for prostate cancer and radiographic progression. Subjects will be followed for a maximum of 3 years from first dose. The study will end when the last subject has been followed for 1 year from date of first dose. Radiographic imaging will end when the patient has developed a radiographic progression, or initiated subsequent anti-neoplastic therapy. Reasonable effort should be made to contact any subject lost to follow-up during the course of the study in order to complete study related assessments and retrieve any outstanding data and study drug. Following unsuccessful telephone contact, an effort to contact the subject by mail using a method that provides proof of receipt should be attempted. Such efforts should be documented in the source documents.

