12.2 Liver Safety Monitoring and Assessment

Any subject enrolled in a clinical study with active drug therapy and reveals an increase of serum aminotransferases (AT) to $> 3 \times \text{ULN}$ (to $> 5 \times \text{ULN}$ in subjects with liver metastases), or bilirubin $> 2 \times \text{ULN}$, should undergo detailed testing for liver enzymes (including at least ALT, AST, ALP, and TBL). Testing should be repeated within 48-72 hours of notification of the test results. For studies for which a central laboratory is used, alerts will be generated by the central lab regarding moderate and severe liver abnormality to inform the investigator, study monitor and study team. Subjects should be asked if they have any symptoms suggestive of hepatobiliary dysfunction.

Definition of Liver Abnormalities

Confirmed abnormalities will be characterized as moderate and severe where ULN:

	ALT or AST		Total Bilirubin
Moderate	> 3 x ULN (in patients without liver metastases), > 5 x ULN (in patients with liver metastases)	or	> 2 x ULN
Severe*	> 3 x ULN	and	> 2 x ULN

In addition, the subject should be considered to have severe hepatic abnormalities for any of the following:

- ALT or AST $> 8 \times ULN$
- ALT or AST > 5 \times ULN for more than 2 weeks (in the absence of liver metastases)
- ALT or AST > 3 × ULN and INR > 1.5 (If INR testing is applicable/evaluated)
- ALT or AST $> 3 \times$ ULN with the appearance of fatigue, nausea, vomiting, right upper quadrant pain or tenderness, fever, rash and/or eosinophilia (> 5%).

The investigator may determine that abnormal liver function results, other than as described above, may qualify as moderate or severe abnormalities and require additional monitoring and follow-up.

Follow-up Procedures

Confirmed moderate and severe abnormalities in hepatic functions should be thoroughly characterized by obtaining appropriate expert consultations, detailed pertinent history, physical examination and laboratory tests. The site should complete the Liver Abnormality Case Report Form (LA-CRF) or appropriate document. Subjects with confirmed abnormal liver function testing should be followed as described below.

Confirmed moderately abnormal LFTs should be repeated 2-3 times weekly then weekly or less if abnormalities stabilize or the study drug has been discontinued and the subject is asymptomatic.

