Severe hepatic liver function abnormalities as defined above, in the absence of another etiology may be considered an important medical event and may be reported as a Serious Adverse Event (SAE). The Sponsor should be contacted and informed of all subjects for

whom severe hepatic liver function abnormalities possibly attributable to study drug are observed.

To further assess abnormal hepatic laboratory findings, the investigator is expected to:

- Obtain a more detailed history of symptoms and prior or concurrent diseases. Symptoms and new onset-diseases should be recorded as 'adverse events' on the AE page of (e)CRF. Illnesses and conditions such as hypotensive events, and decompensated cardiac disease that may lead to secondary liver abnormalities should be noted. Non-alcoholic steatohepatitis (NASH) is seen in obese hyperlipoproteinemic, and/or diabetic patients and may be associated with fluctuating aminotransferase levels. The investigator should ensure that the medical history form captures any illness that pre-dates study enrollment that may be relevant in assessing hepatic function.
- Obtain a history of concomitant drug use (including non-prescription medication, complementary and alternative medications), alcohol use, recreational drug use, and special diets. Medications, including dose, should be entered on the concomitant medication page of the (e)CRF. Information on alcohol, other substance use, and diet should be entered on the LA-CRF or an appropriate document.
- Obtain a history of exposure to environmental chemical agents.
- Based on the subject's history, other testing may be appropriate including:
 - o acute viral hepatitis (A,B, C, D, E or other infectious agents).
 - o ultrasound or other imaging to assess biliary tract disease
 - o other laboratory tests including INR, direct bilirubin
- Consider gastroenterology or hepatology consultations.
- Submit results for any additional testing and possible etiology on the LA-CRF or an appropriate document.

Study Discontinuation

In the absence of an explanation for increased LFT's, such as viral hepatitis, pre-existing or acute liver disease, presence of liver metastases, or exposure to other agents associated with liver injury, the subject may be discontinued from the study. The investigator may determine that it is not in the subject's best interest to continue study enrollment. Discontinuation of treatment should be considered if:

- ALT or AST $> 8 \times ULN$

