- ALT or AST $> 5 \times$ ULN for more than 2 weeks (in subjects without liver metasteses
- ALT or AST $> 3 \times$ ULN and TBL $> 2 \times$ ULN or INR > 1.5 (If INR testing is applicable/evaluated)
- ALT or AST $> 5 \times$ ULN and (TBL $> 2 \times$ ULN in patients with liver metasteses)
- ALT or AST $> 3 \times$ ULN with the appearance of fatigue, nausea, vomiting, right upper quadrant pain or tenderness, fever, rash and/or eosinophilia (> 5%).

In addition, if close monitoring for a subject with moderate or severe hepatic laboratory tests is not possible, drug should be discontinued.

*Hy's Law Definition-Drug-induced jaundice caused by hepatocellular injury, without a significant obstructive component, has a high rate of bad outcomes, from 10–50% mortality (or transplant)." The two "requirements" for Hy's Law are:1. Evidence that a drug can cause hepatocellular-type injury, generally shown by an increase in transaminase elevations higher 3 times the ULN ("2 x ULN elevations are too common in treated and untreated patients to be discriminating"). 2. Cases of increased bilirubin (at least 2 x ULN) with concurrent transaminase elevations at least 3 x ULN and no evidence of intra- or extra-hepatic bilirubin obstruction (elevated alkaline phosphatase)or Gilbert's syndrome. [Temple R. Hy's law: predicting serious hepatotoxicity. Pharmacoepidemiol Drug Saf. 2006 Apr;15(4):241-3.]

Reference

Guidance for Industry titled "Drug-Induced Liver Injury: Premarketing Clinical Evaluation" issued by FDA on July 2009.

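### Protocol 6.1 names isolated AST, ALT or bilirubin > 5 × ULN as a removal example but not ALT or AST > 3 × ULN with bilirubin > 2 × ULN, and no section requires a hold or stop for that combined pattern

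*Protocol*

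**What the plan says.** Protocol 6.1 opens its list with "The following events will result in the removal of subjects from enzalutamide therapy". The first entry, on adverse events, illness and toxicity, is conditional: it applies where continued "administration of study drug is deemed not in the subject's best interest" by the investigator and/or the sponsor. Examples follow, and the only hepatic one is "AST, ALT, or total bilirubin > 5 times ULN". No combined transaminase and bilirubin criterion appears.

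Appendix 12.2 grades liver findings: "Confirmed abnormalities will be characterized as moderate and severe where ULN". ALT or AST > 3 × ULN with total bilirubin > 2 × ULN falls in the Severe row. Unlike the Moderate row, that row has no separate threshold for liver metastases. An asterisk leads from it to the Hy's Law note. After a first abnormal value, "Testing should be repeated within 48-72 hours of notification of the test results". On stopping, the appendix uses three strengths of wording:

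- Without an explanation such as viral hepatitis, liver metastases "or exposure to other agents associated with liver injury, the subject may be discontinued from the study".
- "Discontinuation of treatment should be considered if" introduces a list that includes the combined pattern.
- The one firm instruction is conditional: "if close monitoring for a subject with moderate or severe hepatic laboratory tests is not possible, drug should be discontinued".

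Protocol 5.4 requires sponsor contact within 24 hours for a confirmed, marked hepatic abnormality. Protocol 5.1.2 interrupts dosing only for toxicity of Grade 3 or more that is judged related and cannot be ameliorated. SAP 7.5.2.1 counts subjects with the combined pattern in one sample but attaches no action.

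**The concern.** The pattern that the protocol itself rates as worse is not among the named removal examples, while a finding it can rate as only Moderate is. A site working from 6.1 would find isolated ALT 5.1 × ULN there and would not find ALT 4 × ULN with bilirubin 2.5 × ULN. A site working from 12.2 would find the second rated Severe, with the decision to stop left open. Neither section cites the other or says which governs.

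Two steps have no stated action: dosing between the first abnormal result and its repeat, and dosing after the pattern is confirmed with no other cause found. This is a matter of participant safety. The primary endpoint and its analysis are untouched. Protocol 10.1 provides for no monitoring committee, so these decisions rest with the investigator and the sponsor.

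**Working it through.** The plan gives no figure to reproduce. The check compares the rules, then sizes what they leave open.

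**1. Rules side by side.** Values are multiples of ULN. The 6.1 example is met if either value is > 5. The 12.2 list for considering discontinuation is met by ALT/AST > 8; by > 5 for more than 14 days without liver metastases; by > 3 with bilirubin > 2; or by > 5 with bilirubin > 2 with liver metastases. The INR and symptom triggers are left out. The proposed line is ALT/AST > 3 with bilirubin > 2, without liver metastases.

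| ALT/AST | Bilirubin | Days | Liver metastases | 6.1 example | 12.2 rating | 12.2 consider stopping | Proposed line |
|---|---|---|---|---|---|---|---|
| 4 | 2.5 | 3 | no | no | Severe | yes | yes |
| 5 | 5 | 3 | no | no | Severe | yes | yes |
| 5.1 | 1 | 3 | no | yes | Moderate | no | no |
| 6 | 1 | 15 | no | yes | Severe | yes | no |
| 4 | 2.5 | 3 | yes | no | Severe | yes | no |
| 6 | 2.5 | 3 | yes | yes | Severe | yes | no |

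Rows 1 and 3 show the mismatch. The range that is Severe in 12.2 but unnamed in 6.1 is ALT or AST > 3 to 5 with bilirubin > 2 to 5. Row 3 also shows that the sections differ on isolated transaminases: 6.1 sets no duration, while 12.2 waits for > 8, or for more than two weeks above 5 without liver metastases.

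**2. Overlap with 5.1.2.** This depends on Grade 3 cut-points that the documents do not print. Under assumed cut-points for ALT/AST and bilirubin:

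- 5 and 5 × ULN: the whole range is left open.
- 5 and 3 × ULN: ALT/AST > 3 to 5 with bilirubin > 2 to 3 is left open.
- 3 and 2 × ULN: nothing is left open, provided the toxicity is judged related and cannot be ameliorated.

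**3. Timing.** Protocol 5.4.3 schedules liver tests at Screening, Week 1, Week 13, Week 25 and every 12 weeks after, with further tests at unscheduled visits and at Safety Follow-Up. The on-treatment gaps are 85 − 1 = 84 days and 169 − 85 = 84 days. With the ± 3 day windows the widest is 172 − 82 = 90 days. A sample that first shows the pattern may therefore follow about 12 weeks of dosing. A hold at detection does not shorten that gap, but it makes a stated action at detection more useful.

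**4. Expected number.** The documents give no rate, and the common events in Protocol 1.3 include no hepatic item. For an assumed per-subject risk p, the chance of at least one case in 40 is 1 − (1 − p)^40:

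| p (assumed) | Chance of at least one case |
|---|---|
| 0.1% | 3.9% |
| 0.5% | 18.2% |
| 1% | 33.1% |
| 2% | 55.4% |

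**5. What a short hold does to exposure.** With the mean half-life of 5.8 days in Protocol 1.2 and simple exponential decay of the parent drug, 2^(−2/5.8) = 0.79 and 2^(−3/5.8) = 0.70. About 70–79% of the level remains after two to three days. The hold costs little treatment. It also lowers exposure only modestly, so its main value is that restarting becomes a deliberate decision.

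**The case against.** The strongest reply is that the pattern is already handled. The 6.1 items are examples under a best-interest judgement, and that same entry requires removal for the combined pattern once the judgement is made. The investigator may also end a subject's participation at any time if the clinical condition warrants it. Protocol 5.4, 5.4.2.1 and 5.5.8 all send sites to 12.2, which provides the Severe rating, the repeat, the work-up, possible SAE reporting and a prompt to consider stopping. Discretion is defensible in a metastatic population: liver metastases are a listed explanation for raised liver tests, and exclusion 14 admits bilirubin up to just under 2.5 × ULN, so a subject can enter already above the 2 × ULN limb.

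Most of this stands. A reader might infer that 6.1 compels removal for every isolated value > 5 × ULN while the plan keeps a subject with the combined pattern on drug. The documents do not support that, because both provisions leave room for judgement and nothing prevents stopping. A reader might also apply the 10–50% mortality or transplant figure in 12.2 to anyone with the two laboratory values. The note attaches it to drug-induced hepatocellular jaundice without a significant obstructive component, which is narrower.

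The reply does not supply the missing action. The 24-hour contact in 5.4 is notification, and it starts only once the abnormality is confirmed. No section tells the site what to do with dosing during the repeat, or makes stopping the default when the pattern is confirmed and unexplained.

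**Conclusion.** The point holds as a cheap safety improvement worth making. The stopping language is weaker for the pattern that the protocol rates as worse, and dosing during the repeat is unaddressed. The gap is at most ALT or AST > 3 to 5 × ULN with bilirubin > 2 to 5 × ULN, less whatever 5.1.2 covers, which cannot be settled from the documents. Few cases are expected, and the number cannot be derived: the probabilities above rest wholly on assumed risks. The conclusion takes the 6.1 laboratory items as non-exhaustive examples and takes a marked abnormality in 5.4 to include the Severe category of 12.2.

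**What to change.** 1. **Add a hold to 5.1.2.** For subjects without liver metastases: if ALT or AST is > 3 × ULN with total bilirubin > 2 × ULN in the same sample (and above baseline if baseline bilirubin exceeded ULN), hold enzalutamide pending the 48–72 hour repeat in 12.2. Dosing may restart after discussion with the sponsor if the pattern is not confirmed or another cause is found. The hold belongs here because 6.1 deals with permanent discontinuation.
2. **Add a removal line to 6.1.** Remove the subject if that pattern is confirmed with no other explanation. State that this line, and not the temporary hold, is a withdrawal criterion for deviation category PD2.
3. **Leave subjects with liver metastases** under the existing 6.1 example of > 5 × ULN and the 12.2 triggers.
4. **Cross-reference 5.1.2, 6.1 and 12.2**, and have the sponsor state which section governs isolated ALT or AST > 5 × ULN. A blanket rule that the stricter section applies would remove the duration and liver-metastasis allowances in 12.2 without argument.

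The cost is a protocol amendment with IRB/IEC approval before use (Protocol 8.3.3), and an interruption of at least 48–72 hours in a few subjects who prove to have another cause. No new test is needed, because 12.2 already asks for the repeat. No SAP change is needed, because SAP 7.3.1 already counts dose interruptions and discontinuations.

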- 2. Use of any antineoplastic treatment post-chemotherapy, including but not limited to aminoglutethimide, ketoconozole, abiraterone acetate, Rad-223, sipuleucel-T, or enzalutamide. Continuing steroids is permitted.
- 3. Palliative radiation therapy within 2 weeks of Day 1, or within 4 weeks of Day 1 if a radionuclide was utilized.
- 4. Use of an investigational agent within 4 weeks of Day 1 visit.
- 5. Major surgery within 4 weeks prior to Day 1 visit.
- 6. History of seizure or any condition that may predispose to seizures (e.g., prior cortical stroke or significant brain trauma) at any time in the past. History of loss of consciousness or transient ischemic attack within 12 months of screening.
- 7. History of clinically significant cardiovascular disease including:
 - a. Myocardial infarction or uncontrolled angina within 3 months;
 - b. History of congestive heart failure NYHA class 3 or 4 in the past, unless a screening echocardiogram or multi-gated acquisition scan performed within three months results in a left ventricular ejection fraction that is $\geq 45\%$;
 - c. History of clinically significant ventricular arrhythmias (e.g., ventricular tachycardia, ventricular fibrillation, torsades de pointes);
 - d. History of Mobitz II second degree or third degree heart block without a permanent pacemaker in place.
- 8. Clinically significant cardiovascular disease at screening including:
 - a. Hypotension as indicated by systolic blood pressure < 86 millimeters of mercury (mm Hg) at screening;
 - b. Bradycardia as indicated by a heart rate of < 45 beats per minute on the screening electrocardiogram (ECG) and on physical examination;
 - c. Uncontrolled hypertension as indicated by at least 2 consecutive measurements of a

resting systolic blood pressure > 170 mmHg or diastolic blood pressure > 105 mmHg at the screening visit.

- 9. Subject has a known or suspected hypersensitivity to enzalutamide or any components of the formulation used.
- 10. Severe concurrent disease, infection, or co-morbidity that, in the judgment of the investigator, would make the patient inappropriate for enrollment.
- 11. Known or suspected brain metastasis or leptomeningeal disease.
- 12. Gastrointestinal disorder affecting absorption (e.g., gastrectomy, active peptic ulcer disease within last 3 months);
- 13. Absolute neutrophil count < 1,500/ μ L, platelet count < 75,000/ μ L, or hemoglobin < 5.6 mmol/L (9 g/dL) at screening.

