- 12. Gastrointestinal disorder affecting absorption (e.g., gastrectomy, active peptic ulcer disease within last 3 months);
- 13. Absolute neutrophil count < 1,500/μL, platelet count < 75,000/μL, or hemoglobin < 5.6 mmol/L (9 g/dL) at screening.
- 14. Total bilirubin or alanine aminotransferase (ALT) or aspartate aminotransferase (AST) \geq 2.5 times ULN at screening.
- 15. Creatinine $> 177 \mu \text{mol/L}$ (> 2 mg/dL) at screening.
- 16. Albumin $\leq 30 \text{ g/L} (3.0 \text{ g/dL})$ at screening.

17. Treatment with abiraterone acetate prior to enzalutamide for mCRPC in the prechemotherapy setting. (*Note*: Patients who have received concomitant enzalutamide and abiraterone acetate therapies are not excluded).

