5.1.2 Increase or Reduction in Dose of the Study Drug(s)

Subjects who experience a Grade 3 or greater toxicity considered to be related to enzalutamide that cannot be ameliorated by the use of adequate medical intervention should have their treatment interrupted until the toxicity improves to a Grade 2 or lower severity.

Subjects may subsequently be re-started on study drug at a reduced dose following a discussion between the Investigator and the sponsor.

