7.7 Protocol Deviations

Protocol deviations as defined in Section 8.1.6 Protocol Deviations will be summarized for all enrolled subjects overall as well as by site. A data listing will be provided by site and subject.

The protocol deviation criteria will be uniquely identified in the summary table and listing. The unique identifiers will be as follows:

- PD1 Entered into the study even though they did not satisfy entry criteria,
- PD2 Developed withdrawal criteria during the study and was not withdrawn,
- PD3 Received wrong treatment or incorrect dose,
- PD4 Received excluded concomitant treatment.

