7.2.2 Protocol Deviations

Protocol deviations as defined in the study protocol (Section 8.1.6 Protocol Deviations) will be assessed for all dosed patients. The number and percentage of subjects meeting any criteria will be summarized for each criterion and overall. Subjects deviating from a criterion more than once will be counted once for the corresponding criterion. Any subjects who have more than one protocol deviation will be counted once in the overall summary. A data listing will be provided by site and subject.

The protocol deviation criteria will be uniquely identified in the summary table and listing. The unique identifiers will be as follows:

- PD1 - Entered into the study even though they did not satisfy entry criteria,
- PD2 - Developed withdrawal criteria during the study and was not withdrawn,
- PD3 - Received wrong treatment or incorrect dose,
- PD4 - Received excluded concomitant treatment.

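### Section 6.1 prints the platelet limit for stopping enzalutamide per mL, a factor of 1,000 below the per-microlitre unit used for every other blood-count limit

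*Protocol*

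**What the plan says.** Section 6.1 of the protocol sets out events that lead to removal from enzalutamide. One is an adverse event, illness or toxicity for which the investigator and/or sponsor judges continued treatment not to be in the subject's interest. Examples follow, among them protocol-defined laboratory limits for creatinine, liver tests, neutrophils and platelets. The last two are printed in different units:

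- neutrophils: "Absolute neutrophil count $< 750/\mu$ L"
- platelets: "Platelet count < 50,000/mL"

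Exclusion criterion 13 in Section 3.3 gives the entry limit as "platelet count < 75,000/μL, or hemoglobin < 5.6 mmol/L (9 g/dL) at screening", and the synopsis uses the same unit. No other section of the protocol states a platelet limit for removal, and the SAP gives none.

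The removal criteria also feed a reported table. Protocol Section 7.7 defines the deviation category "PD2 Developed withdrawal criteria during the study and was not withdrawn", and SAP Section 7.2.2 repeats it.

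**The concern.** The two adjacent blood-count limits are in units that differ by a factor of 1,000, and the platelet line is the one that disagrees with the rest of the protocol. At 50 platelets per microlitre the limit would practically never be met, so on a literal reading the protocol has no working numeric platelet limit for stopping the drug.

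Two things depend on it. The first is the stopping rule that the sites follow. The second is the PD2 count: Section 8.1.6 makes this category notifiable to the sponsor, and both documents call for it to be summarised and listed. Whoever classifies deviations needs a single unambiguous limit.

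**Working it through.** The plan derives no figure here, so there is none to reproduce. The check is a unit conversion and a comparison with the other limits.

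**Inputs**

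| Parameter | Entry limit (Section 3.3, criteria 13 to 15) | Removal limit (Section 6.1) |
|---|---|---|
| Platelets | 75,000 per µL | 50,000 per mL as printed |
| Neutrophils | 1,500 per µL | 750 per µL |
| Creatinine | 177 µmol/L (2 mg/dL) | 354 µmol/L (4.0 mg/dL) |
| AST, ALT or bilirubin | 2.5 × ULN | 5 × ULN |

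**Conversion.** 1 mL = 1,000 µL, so 50,000 per mL = 50,000 / 1,000 = 50 per µL.

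**Size of the discrepancy.** 50,000 per µL / 50 per µL = 1,000.

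**Entry limit divided by removal limit**

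- Platelets as printed: 75,000 / 50 = 1,500
- Platelets if the unit is microlitres: 75,000 / 50,000 = 1.5
- Neutrophils: 1,500 / 750 = 2.0
- Creatinine: 354 / 177 = 2.0, taken as removal over entry because high values are the concern (4.0 / 2 = 2.0 in mg/dL)
- AST, ALT or bilirubin: 5 / 2.5 = 2.0, also removal over entry

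The ratios do not prove a common design rule, since 1.5 is not 2.0. They show only that 50,000 per µL is of the same order as the other pairs and that the printed value is not. The evidence that carries the point is the unit itself: per microlitre for platelets at entry, stated twice, and per microlitre for neutrophils on the preceding line.

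**Counts affected by the choice of unit.** A platelet count from 50 to 49,999 per µL meets the limit if the unit is microlitres and does not meet it as printed. A subject kept on drug at 30,000 per µL, for example, would not be a PD2 case on this criterion as printed, but could be one with the corrected unit.

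**The case against.** The strongest objection is that this may not be an error in the protocol at all. It rests on one character, and a micro sign misread as m when the PDF was converted to text would give exactly this result. That possibility stands. It is less likely than a slip in the source, because the micro sign comes through in the creatinine and neutrophil lines of the same list and in exclusion criterion 13.

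The second objection is that nobody would apply the literal value. Entry requires at least 75,000 per µL, and a clinician would read the limit as per microlitre. The limits are also examples under a judgement clause. This fairly lowers the risk to subjects, but the same list calls the values protocol-defined, and a reader's inference does not correct the text.

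The third is that safety is covered elsewhere. Section 5.4.3 schedules platelet counts and requires a physician to judge the clinical significance of out-of-range results. Laboratory values are CTCAE-graded with shift tables (protocol Section 7.5.2, SAP Section 7.5.2), and Section 6.1 lets the investigator end a subject's participation when his condition warrants it. Section 5.1.2 interrupts dosing for "Grade 3 or greater toxicity considered to be related to enzalutamide that cannot be ameliorated". These safeguards are real, but none supplies a numeric platelet limit for removal. Section 5.1.2 covers only related toxicity and leads to interruption with a possible restart, so a low count attributed to marrow disease or prior taxane would fall outside it.

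Finally, the PD2 effect arises only if someone classifies deviations by the printed number, and the sponsor follows up deviations. That is correct, and it keeps the expected effect small.

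**Conclusion.** The point holds. As printed, the platelet limit for removal is 50 per µL, 1,000 times lower than the 50,000 per µL that was almost certainly meant. No other text in either document corrects it. Only the removal rule and the PD2 count are affected. Neither document defines a per-protocol set (protocol Section 7.2.2, SAP Section 5.2), so PD2 status excludes no one from the efficacy analyses, and sample size and efficacy estimates do not change.

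This is a small correction that should be made because it concerns a safety limit and costs almost nothing. Confidence is medium, since the conclusion assumes that the signed protocol carries the same unit as the text available here.

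**What to change.** Check the platelet line of Section 6.1 in the signed protocol. If it does read per mL, change the unit to per µL, so that the limit is a platelet count below 50,000/µL, and notify the sites. Apply that limit when PD2 deviations are classified under protocol Section 7.7 and SAP Section 7.2.2.

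The cost is a one-character amendment and a note to sites. No new data are needed and no analysis changes.
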